#### Device malfunctions

Device malfunctions will be identified among device deficiencies by a medical expert before start of the statistical analysis.

Incidence of observed device malfunctions and the nature of device malfunctions (based on components involved) will be summarized for subjects using the descriptive statistics defined in Section 7.1. The number of subjects with malfunction including percentage based on all subjects enrolled, and the number of events will be provided. In addition, the rate of device malfunctions per 10 patient years and accompanying exact 95% confidence intervals will be calculated, assuming that

---

b Zou, G. (2011). Confidence interval estimation for the Bland-Altman limits of agreement with multiple observations per individual. *Stat Methods Med Res*, S. 0 (0): 1-13.

the number of such device malfunctions is Poisson distributed. The procedure will be analogous to the procedure for incidence rates of AEs (see Section 7.7).

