- Less inflammation: while all patients in the ARGOS-02 trial experienced at least some degree of postsurgical inflammation, in most cases this inflammatory response was similar in intensity and duration to that observed after standard cataract surgery. Most notably, not a single case of hypopyon occurred during the ARGOS-02 trial compared to two cases (33.3%) in the ARGOS-01 trial. There were still five patients (21.7%) who experienced fibrin exudation after surgery

 Implantdata Ophthalmic Products GmbH	Clinical Investigation Plan ARGOS-03	Revision C Page 24 of 67
---------------------------------------------------------------------------------------------------------------------------	-------------------------------------------------------	---------------------------------

(compared to 66.7% in the ARGOS-01 trial), two of which were briefly hospitalized and treated accordingly. All instances of anterior chamber inflammation resolved quickly however and the number of other inflammation related adverse events (corneal edema, cystoid macular edema) was low and comparable to rates reported in literature for cataract surgery alone.

- Less pigment dispersion: pigment dispersion, which may lead to increased intraocular pressure, was reported as adverse event for five out of six patients in the ARGOS-01 and eight out of 22 patients in the ARGOS-02 trial, thus constituting a significant reduction of pigment release to a rate similar to that seen in cataract surgery with sulcus fixed intraocular lenses. Further improvements can be expected, when the level of experience with the redesigned device increases.
- Better performance: concordance between ARGOS-IO measurements and GAT IOP was significantly better than in the ARGOS-01 trial. The mean difference between IOP obtained through ARGOS-IO and GAT was 10.2 mmHg in the ARGOS-01 trial and 2.8 mmHg in the ARGOS-02 trial. The 95% limits of agreement changed from -7.58 mmHg and 30.01 mmHg in the ARGOS-01 trial to -1.7 mmHg and 7.4 mmHg in the ARGOS-02 trial.

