7.1.4 Primary Outcome Variables

Safety:

- Incidence of medical-device related adverse events

 Implantata Ophthalmic Products GmbH	Clinical Investigation Plan ARGOS-03	Revision C Page 43 of 67
--------------------------------------------------------------------------------------------------------------------------	-------------------------------------------------------	---------------------------------

- Incidence of medical-device related serious adverse event.
 - o An AE is considered to be device-related if there is at least a possible relationship to the medical device according to the rating of the investigator
 - o An AE is considered to be serious if it meets any of the criteria defined in Section 9.1.1.2

The analysis will be split by nature, severity and seriousness of medical device related adverse and serious adverse events.

Performance:

- Limits of agreement between IOP measurements made using GAT and the ARGOS-IO system at each study visit.
- Limits of agreement between IOP measurements made using DCT and the ARGOS-IO system at each study visit.
- Incidence of observed device malfunctions and nature of device malfunction (e.g. difference of more than 5 mmHg between ARGOS-IO and GAT, readout error of the Mesograph because of measurements outside -2 and +70mmHG).

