7.2.4 Analysis of Primary Performance Outcome Variables

Limits of Agreement

The Bland-Altman method, which compares the mean of paired measurements to their difference will be used to determine the upper and lower limits of agreement expected to contain 95% of the IOP value pairs obtained with the ARGOS-IO system and GAT. For this purpose, the mean of each series with the respective device will be calculated and used for comparison. The agreement evaluation will be based on the assumption that the measurements are constant within the measurement series but not between measurement series with the same device. The two-sided 95% confidence intervals for each of the agreement limits will be calculated using the Mover method (Zou, 2011) to account for repeated observations. IOP values will be displayed as Bland-Altman plots of individual measurement pairs by measurement technique for each visit and overall as well as mean plots over time.

Because the ARGOS-IO implant is in direct contact with the aqueous humor and gives a digital readout of IOP, it is anticipated to objectively measure the true IOP. In comparison, although GAT is considered the gold standard, it measures IOP indirectly through applanation of the cornea and is known to be influenced by corneal thickness and biomechanical properties (Burr, et al., 2012). In addition, measurements with GAT are known to be subject to operator bias.

Consequently, the absolute IOP values obtained with the ARGOS-IO system are expected to show a systematic shift in measurements compared to those obtained from indirect methods. The Pascal

 Implantdata Ophthalmic Products GmbH	Clinical Investigation Plan ARGOS-03	Revision C Page 46 of 67
---------------------------------------------------------------------------------------------------------------------------	-------------------------------------------------------	---------------------------------

Dynamic Contour Tonometer (DCT) is constructed to alleviate some of the operator bias of GAT measurements as well as eliminate most of the corneal biomechanical influence on IOP readings. Therefore the limits of agreement between the ARGOS-IO system and DTC measurements will be also calculated by the described procedure.

Device Malfunctions

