9.1.4 Device Deficiencies

The investigator will record all observed device deficiencies by completing a Device Deficiency Form. The reporting modalities are defined in ISO 14155:2011 and MEDDEV 2.7/4 in line with the requirements of Annex X of Directive 93/42/EEC and its amendment Directive 2007/47/EC, Annex 7 of 90/385/EEC and local laws and regulations.

All device deficiencies must be reported to the sponsor immediately. Any Investigational Medical Device Deficiency that might have led to a SAE if a) suitable action had not been taken or b) intervention had not been made or c) if circumstances had been less fortunate must be reported as described in Table 8.6.3 following the SAE reporting modalities.

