### 6.3 Primary Performance Variables

The following primary performance variables are planned to be evaluated:

- Limits of agreement between IOP measurements made using GAT and the ARGOS-IO system at each study visit
- Limits of agreement between IOP measurements made using DCT and the ARGOS-IO system at each study visit
- Incidences of observed device malfunctions and nature of device malfunction

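### The SAP's primary malfunction count omits the CIP's own example, an ARGOS-IO versus GAT difference above 5 mmHg, and has no rule for deriving it from the paired readings

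*SAP*

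**What the plan says.** CIP 7.1.4 lists the incidence and nature of device malfunctions among the primary performance outcomes. Its examples, introduced by e.g., are: "difference of more than 5 mmHg between ARGOS-IO and GAT, readout error of the Mesograph because of measurements outside -2 and +70mmHG".

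SAP 6.3 keeps the variable without the examples: "Incidences of observed device malfunctions and nature of device malfunction". SAP 7.5 then fixes the source of the count: "Device malfunctions will be identified among device deficiencies by a medical expert before start of the statistical analysis". It classifies the nature of a malfunction by the component affected, and reports the number of subjects, the number of events, and a rate per 10 patient years with an exact Poisson interval. It states no criterion for the expert.

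Deficiencies enter the data through the site. CIP 9.1.4 says: "The investigator will record all observed device deficiencies by completing a Device Deficiency Form". CIP 6.4.3.2 has staff record deficiencies at each visit, but no site-facing section gives a 5 mmHg trigger. Table 1 schedules deficiency recording at V02 to V07 only, while paired GAT and ARGOS-IO series are taken at all seven visits.

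For the agreement analysis, SAP 7.5 already derives, per subject and visit, the mean of the ARGOS-IO values minus the mean of the GAT values in the same series.

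SAP 2.11 requires a non-editorial change from the planned analysis to be justified and documented. SAP section 8 lists only the change to the limits-of-agreement method. The SAP document history describes the malfunction wording as a clarification.

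**The concern.** The CIP's first example can be checked against numbers the trial collects at every visit. Under SAP 7.5 a pair more than 5 mmHg apart becomes a malfunction only if a site files a form and the expert then accepts it. A sensor that works but reads inaccurately also has no obvious place in a classification by component.

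The study is unmasked (SAP 2.8). The expert's selection need only precede the statistical analysis, so it may be made with all readings available. CIP 7.2.4 also says that ARGOS-IO values are "expected to show a systematic shift in measurements compared to those obtained from indirect methods". That could make a large difference look normal rather than reportable, although this is an inference about site behaviour.

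At stake is the meaning of a primary performance result. A reader of the report who knows CIP 7.1.4 would assume that differences above 5 mmHg are in the malfunction rate. Under the SAP they may or may not be, and nothing planned shows how many were left out.

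**Working it through.** **1. Inputs.** CIP 4.2: mean ARGOS-IO minus GAT difference of 2.8 mmHg in ARGOS-02 (95% limits −1.7 to 7.4) and 10.2 mmHg in ARGOS-01 (−7.58 to 30.01). CIP 7.2.7: at most 21 + 5 = 26 patients. CIP 6.4.3: seven visits. CIP 6.3.4: three years of follow-up, so at most 26 × 3 = 78 patient years. Retention is not given; 100% and 60% are assumed.

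**2. Check of the stated figures.** The midpoint of the limits should equal the mean.
- ARGOS-02: (7.4 − 1.7)/2 = 2.85 against the stated 2.8, which agrees within rounding.
- ARGOS-01: (30.01 − 7.58)/2 = 11.2 against the stated 10.2, which does not agree. Using 11.2 instead would move the ARGOS-01 proportion below only from 0.763 to 0.787.

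**3. SD of the differences** = (upper − lower)/(2 × 1.96).
- ARGOS-02: 9.1/3.92 = 2.32.
- ARGOS-01: 37.59/3.92 = 9.59.

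**4. Proportion beyond 5 mmHg**, assuming normal differences: P = 1 − Φ((5 − mean)/SD) + Φ((−5 − mean)/SD).
- ARGOS-02 agreement: 0.172.
- ARGOS-01 agreement: 0.763.
- Zero bias, SD 2.32: 0.031.
- Zero bias, SD 9.59: 0.602.

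**5. Expected visit pairs beyond 5 mmHg**

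| Scenario | ARGOS-02 | ARGOS-01 | Total |
|---|---|---|---|
| Earlier agreement persists, V01–V07 | 147 × 0.172 = 25.3 | 35 × 0.763 = 26.7 | 52.0 of 182 |
| Same, V02–V07 only | 126 × 0.172 = 21.7 | 30 × 0.763 = 22.9 | 44.6 of 156 |
| Same as first row, 60% retention | 15.2 of 88 | 16.0 of 21 | 31.2 of 109 |
| Zero bias, each generation keeps its SD | 4.6 of 147 | 21.1 of 35 | 25.7 of 182 |
| Zero bias, ARGOS-02 SD for all | | | 182 × 0.031 = 5.7 |

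**6. What the SAP endpoint could read.** With no forms filed, the rate is 0. The exact 95% upper limit is (χ² quantile 0.975 on 2 df)/2 = 3.69 events, and 10 × 3.69/78 = 0.47 per 10 patient years. Counting 52 flagged visits as events would give 10 × 52/78 = 6.7 per 10 patient years (exact 95% CI 5.0 to 8.7). That interval treats repeated flags in one patient as independent, which they are not, so it is shown for scale only.

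**The case against.** The 5 mmHg item is an example, not a rule. The CIP does not say whether it applies to a reading, a series or a visit, or whether the difference is signed. CIP 7.2.4 never says that malfunctions are to be derived from IOP readings. Taking malfunctions from deficiencies is also the CIP's own structure: section 9.1.1.6 makes malfunctions a subset of deficiencies. All of this stands. It is a reason for the SAP to settle how the example is used, and the SAP is silent.

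A reader might infer that the endpoint will read near zero while the trial's readings show dozens of malfunctions. The documents do not support that:
- They contain no ARGOS-03 readings, so any count is a projection.
- Zero forms is a worst case. Inadequate performance is a deficiency under CIP 9.1.1.6, sites must record and report deficiencies (9.1.4), and sensor function is checked against GAT at least yearly and adjusted if necessary (6.1.2).
- More than half of the 52 comes from five first-generation patients. CIP 4.2 links that prototype's aberrant readings to distortion in the first months after cataract surgery, so carrying its spread forward is an assumption.

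Nor would large differences be hidden. SAP 7.5 plans limits of agreement, Bland-Altman plots and per-visit summaries of the differences. They remain visible there, but no proportion beyond 5 mmHg is planned and they are not counted as malfunctions.

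A mechanical count has its own weakness. CIP 7.2.4 attributes corneal and operator error to GAT, and CIP 3.3.3 cites about ±5 mmHg imprecision in repeated IOP measurements. Some flags would be GAT error, and one stable offset could be flagged up to seven times. This stands, and it shapes the fix.

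Finally, SAP section 1 says it elaborates CIP Revision B, while the CIP supplied is Revision C. If Revision B lacked the example, the SAP did not drop it. The SAP would still need aligning with the current CIP.

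**Conclusion.** The mismatch holds. For a primary performance variable, the SAP omits an example that the CIP names, counts only filed deficiencies selected by an expert without written criteria, and does not declare a departure from CIP 7.1.4 in section 8. The malfunction count can therefore miss CIP-named malfunctions that lie in the paired readings.

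The size is uncertain: from about 6 to about 52 of 182 pairs at full enrolment and retention. The upper figure assumes that earlier agreement persists. The lower assumes that adjustment removes all bias and that every patient has the ARGOS-02 SD. Both assume normal differences, and that the CIP 4.2 limits apply to series means, which that section as supplied does not say. The share of such pairs that sites would file is unknown.

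The study is exploratory, with no hypothesis test. The consequence is an ambiguous primary result, not an invalid one.

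**What to change.** In SAP 7.5, use the per-visit difference already derived. For each patient and scheduled visit, flag |mean ARGOS-IO of the post-GAT series − mean GAT| > 5 mmHg, whether or not a form exists. Report the number and percentage of patients and of visits flagged, in a separate row beside the expert-identified malfunctions. Base any rate per 10 patient years on the first flag per patient, or show it separately. Do not pool flagged visits into the Poisson malfunction rate, because repeated flags in one patient are not independent. Add a footnote that some flags will reflect GAT error.

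Give the expert written criteria for the other deficiencies before selection starts.

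If the sponsor no longer treats a difference above 5 mmHg as a malfunction, say so with the reason in SAP section 8, and still report the proportion of pairs beyond 5 mmHg next to the limits of agreement.

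The cost is SAP wording and one table row from data already collected. The downside is that the performance result may look less favourable. If the database has already closed, SAP 2.11 gives the route: document and justify the change at least in the final report, marked as made after close.

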## 7.6 Evaluation of Secondary Variables

### Progression analysis

Summary statistics for raw values and change over time will be provided for visual field, cup/disc ratio and IOP (for all types of measurements) by eye and visit. Frequency tabulations (absolute and relative) will be prepared for OCT results for the optic nerve over the course of the study, by eye and visit. The denominator for the calculation of relative frequencies will be the number of subjects attending the respective visit.

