7.2.5 Analysis of Secondary Outcome Variables

Progression of visual field, cup/disc ratio, OCT results for the optic nerve and IOP over the course of the study will be summarized for the subjects by eye and visit using the descriptive statistics defined at the beginning of Section 7.2. The Change from baseline will be calculated for continuous outcome variables and, where meaningful, shift-tables for categorical variables.

Analysis of changes in glaucoma medication and number of unscheduled visits due to self-measured increased IOP will be analyzed analogue to the analysis for incidence rates of AEs. The rate of changes in medication / unscheduled visits per 10 patient years and accompanying exact 95% confidence intervals will be calculated, assuming that the number of such events is Poisson distributed.

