### 6.4 Secondary Performance Variables

The following secondary variables are planned to be evaluated:

- Glaucoma progression over the course of the study evaluated by change in
  - visual field
  - cup/disc ratio (horizontal and vertical)
  - OCT results for the optic nerve
  - IOP
- Number of changes in glaucoma medication
- Number of unscheduled visits due to self-measured increased IOP

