## 7. Statistical Analysis Methods

### 7.1 Descriptive Statistics

The default summary statistics for quantitative variables will be the number of non-missing observations (n), number of missing observations (miss), arithmetic mean, standard deviation (SD), lower quartile (Q1), upper quartile (Q3), minimum (min), median, and maximum (max) for those patients with data available.

For categorical variables, the number (n) and percentage (%) of patients per category will be the default summary presentation, and, if applicable, the number of missing values is provided in a “Missing” category. For the number of missing values, only patients that attended the respective visit will be counted. Percentages will be calculated using a denominator of all patients with non-missing data. If necessary, the denominator will be specified in a footnote to the tables for clarification.

All tables including calculation of change over time (Visit 01 vs Visit 02 – Visit 07) will also include summary tabulations for the raw values of the respective variable analysed.

In case of analyses per eye, results will be grouped by study eye / fellow eye instead of right eye / left eye.

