## 7.3 Data Derivation

### 7.3.1 Change Over Time

Whenever the change over time is analyzed, the result at the start of the time period of interest (usually Visit 01) is subtracted from the result at the end of the time period of interest (usually Visit 02 – Visit 07)

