## Listings

12.2	Subject data listings
12.2.1	Disposition of subjects
12.2.1.1	Site numbers and principal investigators
12.2.1.2	Informed consent
12.2.1.3	Visit dates and discontinuation
12.2.2	Protocol deviations
12.2.3	Demographics and other patient characteristics
12.2.4	Medical history and concomitant diseases
12.2.4.1	Medical history
12.2.4.2	Concomitant diseases
12.2.5	Concomitant medications
12.2.5.1	Glaucoma medication
12.2.5.2	Other concomitant medications
12.2.6	Performance
12.2.6.1	IOP measurements by visit
12.2.6.2	Device malfunctions
12.2.6.3	Glaucoma progression by visit
12.2.6.4	Unscheduled visits
12.2.7	Safety data
12.2.7.1	Adverse events listing
12.2.8	Other data
12.2.8.1	Best corrected visual acuity by eye and visit
12.2.8.2	National Eye Institute Vision-related Quality of Life Questionnaire (NEI VFQ-25) by visit
12.2.8.3	Device deficiencies
12.2.8.4	Ophthalmic examinations
12.2.8.4.1	Abnormalities detected by slit-lamp microscopy by eye and visit

- 12.2.8.4.2 Abnormalities detected by funduscopy by eye and visit
- 12.2.8.4.3 Gonioscopy results by eye and visit
- 12.2.8.4.4 Other examinations
- 12.2.8.5 Position of IOL and ARGOS-IO pressure sensor by visit
- 12.2.8.6 Comparative measurements performed in the clinic between study end of ARGOS-01/ARGOS-02 and Visit 01 (GAT vs. ARGOS-IO)

The selection, naming and numeration of the listings is not mandatory but might be adapted in accordance with the described analyses in this SAP.

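### SAP 7.6 summarises glaucoma progression visit by visit but gives no rate per eye and no count of worsening eyes, although seven visual fields per eye are scheduled

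*SAP*

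**What the plan says.** Both documents list the impact of self-monitoring on glaucoma progression as a secondary objective, judged by visual field, cup/disc ratio, optic-nerve OCT and IOP (protocol 5.1.2, SAP 2.4.3). SAP 6.4 sets the variable as "Glaucoma progression over the course of the study evaluated by change in" those four measures.

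The analysis is in SAP 7.6, with results split by eye and visit: "Summary statistics for raw values and change over time will be provided for visual field, cup/disc ratio and IOP (for all types of measurements"). Optic-nerve OCT is handled differently: "Frequency tabulations (absolute and relative) will be prepared for OCT results for the optic nerve over the course of the study". SAP 7.3.1 defines change so that "the result at the start of the time period of interest (usually Visit 01) is subtracted from the result at the end" of the period. The default summary in SAP 7.1 gives counts of observed and missing values and "arithmetic mean, standard deviation (SD), lower quartile (Q1), upper quartile (Q3), minimum (min), median, and maximum (max"), and it requires raw values beside every change table. The SAP appendix lists "Glaucoma progression by visit" among the subject data listings, though it says the selection of listings may be adapted.

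Protocol 7.2.5 states: "The Change from baseline will be calculated for continuous outcome variables". It also allows shift tables for categorical variables where these make sense. SAP 7.6 does not mention shift tables, and SAP 8 does not record their omission as a change.

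Perimetry is scheduled in both eyes at all seven visits, day 0 to day 1080 (protocol Table 1, SAP Table 1).

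**The concern.** Progression happens in individual eyes. With at most 26 implanted eyes, the result a clinician can read most directly is how fast each eye is changing and how many are getting worse. The planned tables do not give either.

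Each tabulated change compares two single tests. The Visit 07 change makes no use of the five fields between. The by-visit tables do show those fields, but as separate differences that all share the same Visit 01 reading. No table links the seven readings of one eye.

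The safety analysis is not designed to fill the gap. Field progression is not among the adverse events of special interest in protocol 5.3, and neither document expressly routes perimetric worsening into adverse event reporting. A count made later from the listing would need a rule chosen after the data were seen.

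**Working it through.** **Inputs from the documents.** Visits on days 0, 180, 360, 540, 720, 900 and 1080; perimetry in both eyes at each; at most 5 + 21 = 26 patients with one implanted eye each, so at most 52 eyes. The documents state no progression figure to reproduce.

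**Assumptions.** The documents give no test-retest SD (s) for the visual field, so s = 1.0, 1.5 and 2.0 dB are used. Errors are taken as independent and normal, and true change as linear.

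**1. Slope against two-point change.** Spacing h = 180/365.25 = 0.493 years; follow-up T = 6h = 2.96 years. The sum of squared time deviations for seven visits is 28h² = 6.80.
- Two-point change, Visit 07 minus Visit 01: variance 2.00 s².
- Three-year change from the slope: T² s²/(28h²) = 36/28 s² = 1.29 s².
- Ratio 1.29/2.00 = 0.64, so 36% less noise variance.

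| s (dB) | SE of slope, s/√6.80 (dB/year) | SE of two-point rate, s√2/T (dB/year) |
|---|---|---|
| 1.0 | 0.38 | 0.48 |
| 1.5 | 0.58 | 0.72 |
| 2.0 | 0.77 | 0.96 |

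**2. What the planned summaries would show.** Suppose 4 of 26 study eyes lose 6 dB over the study and 22 are stable. Mean change = -6 × 4/26 = -0.92 dB. Simulating Visit 07 minus Visit 01 (error SD s√2) gives these expected minima:

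| s (dB) | No fast eye | One fast eye | Four fast eyes |
|---|---|---|---|
| 1.0 | -2.8 | -6.0 | -7.5 |
| 2.0 | -5.6 | -7.1 | -9.0 |

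At s = 2.0 the 5% to 95% ranges of the minimum are -8.2 to -3.5, -10.7 to -4.3 and -12.3 to -6.1 dB, which overlap heavily. The median with four fast eyes is about -0.6 dB. At s = 1.0 the minimum does signal that a fast eye exists, but it does not distinguish one such eye from four.

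With two fast eyes at -1.5 dB/year, 24 at -0.3 dB/year and s = 2.0, the minimum belongs to a truly fast eye in only 45% of runs.

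**3. What a per-eye flag would deliver.** Flag an eye when the 95% confidence interval of its slope lies wholly below zero (t distribution, number of fields minus 2 degrees of freedom). With Visits 01 to 04 only, the sum of squared deviations is 5h² = 1.21. Probability of flagging an eye truly losing 2 dB/year:

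| Fields | s = 1.0 | s = 1.5 | s = 2.0 |
|---|---|---|---|
| 7 | 98% | 79% | 56% |
| 4 | 25% | 14% | 10% |

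Chance flags among truly stable eyes: 0.025 × 26 = 0.65 study eyes, or 0.025 × 52 = 1.3 over both eyes. Flagging cup/disc ratio as well would make 104 eye-measure checks and 104 × 0.025 = 2.6 expected chance flags.

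**The case against.** A reader might infer that progression is reported only as a group mean and that fast eyes would therefore vanish. The documents do not support that. SAP 7.1 prints SD, quartiles, minimum and maximum with raw values; optic-nerve OCT is tabulated as frequencies; SAP 7.8 tabulates optic-nerve abnormalities on funduscopy by eye; and a subject-level progression listing is planned. In the four-eye example, the planned SD of change would rise from about 2.8 to 3.6 dB at s = 2.0, and the minimum would belong to a fast eye in about 92% of runs.

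Nor do patients who leave early contribute nothing. They are missing from the Visit 07 change, but SAP 5.1 and 5.2 use data as available, so they count at every visit they attended.

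The study is declared exploratory and descriptive, and SAP 7.6 largely carries out protocol 7.2.5. The shift tables were discretionary and restricted to categorical variables, so leaving them out weighs little. The primary safety analysis also counts eye-related adverse events by eye.

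A flag based on an interval excluding zero has limits too. It is not a clinical threshold, it depends on each eye's noise, and with four fields it would miss most eyes losing 2 dB/year. An eye drifting at an assumed -0.3 dB/year would be flagged about 9% of the time at s = 1.0.

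All of this stands, and it limits both the weight of the point and the form of the fix. It does not supply a rate per eye or a count. The minimum describes one eye, and the listing carries no rule for separating worsening from noise.

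**Conclusion.** The point holds in a limited form. The planned output describes the distribution at each visit and lists the subject data, but it contains no per-eye rate, no number of worsening study or fellow eyes, and no shift tables. Fast eyes would be diluted in the mean and median and left unlabelled elsewhere.

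The gain from a slope is 36% less noise variance for the three-year change. That ratio follows from the visit schedule and assumes independent errors of equal variance and linear change. The detection rates and the behaviour of the minimum also depend on the assumed test-retest SDs and rates of loss.

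A slope table would describe progression; it would not isolate the effect of self-monitoring. The objective is secondary, the study is exploratory and no stated figure is wrong, so this is a cheap improvement.

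**What to change.** In SAP 7.6, under the progression analysis:
- Add a least-squares slope of visual-field mean deviation (dB/year) with 95% confidence interval for each eye, using all scheduled fields. SAP 7.8 already summarises visual field deviation; confirm that mean deviation is the recorded index.
- Show the number of fields behind each slope, and the distribution of slopes by study and fellow eye.
- As a descriptive supplement, give the number and percentage of eyes whose interval lies wholly below zero. State that an unflagged eye, especially one with few fields, is not thereby shown to be stable.
- For cup/disc ratio, report change or slope descriptively without a significance flag. The flag has not been evaluated for this measure, and it would add chance flags.
- Keep the change-from-Visit-01 tables, and record in SAP 8 that the shift tables of protocol 7.2.5 are not carried over, or restore them where they make sense.

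The cost is SAP wording and one extra table from data already scheduled. About 0.65 of 26 stable study eyes (1.3 of 52 eyes) would be flagged by chance, and detection is low for eyes with few fields. No hypothesis test is introduced, so the descriptive design is unchanged.
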